**Prospective surveillance for very early hepatocellular carcinoma
(PRECAR): a study protocol for an observational multicenter cohort
trial**

NCT number: 03588442

Date:2020.4.30

Version: v1.0

Abstract

Background: Approximately 20% patients are diagnosed to hepatocellular carcinoma at early stage, when effective treatments are feasible, and benefit from curative therapeutic approaches, such as hepatic resection and liver transplantation. Biannual ultrasound is recommended for patients with cirrhosis for early diagnosis of hepatocellular carcinoma. However, limited sensitivity and false-positivity call for development of a new surveillance tool with prior accuracy. This study aims to build a biosignature to stratify high risk population for developing hepatocellular carcinoma and to diagnosis hepatocellular carcinomas at very early stage using biological signature.

Methods: This investigator-initiated, multicenter, observational, cohort trial will enroll 5000 patients with liver cirrhosis and 5000 patients with hepatitis B virus infection. Exclusion criteria include human immunodeficiency virus infection, previous diagnosis of active pulmonary tuberculosis, and pregnancy. Patients will be recruited for 1 year and follow-up investigation will be performed biannually for 3 years to collect demographic and clinical characteristics, blood samples, disease status, and outcome data. Development of hepatocellular carcinoma and overall survival are the primary endpoints, which will be contributed to the development of the biosignature for risk stratification for incidence, diagnosis at very early stage, and survival prediction. The secondary endpoints include development of non-hepatocellular carcinoma hepatic malignancy, liver resection rate, postresection survival, and relapse-free survival.

Discussion: The biosignature will be useful in clinical practice by stratifying patients with cirrhosis or hepatitis B virus infection at high risk for development of hepatocellular carcinoma and diagnosing at very early stage.

Trial registration: ClinicalTrials.gov identifier, NCTxx, first received xx, xx 2018.

Key words: liver cancer, diagnosis, early stage, observational cohort trial, biosignature, prediction model

Introduction

China has among the highest incidence and mortality of hepatocellular carcinoma (HCC) in the world with increasing trend.^{1,2} Prognosis of HCC is variable according to different stages due to feasibility of therapeutic options.³ Radical resection of tumor is recommended for patients with a solitary tumor and preserved liver function without extrahepatic metastasis, whereas liver transplantation provides survival benefits for unresectable cases within Milan criteria (solitary tumor ≤ 5 cm or up to three nodules ≤ 3 cm).^{4,5} In addition, image-guided ablation is the most frequently applied strategy with limitations of size and localization of the tumor.⁶ For multifocal disease without vascular invasion and extrahepatic metastasis, chemoembolization has been suggested to be promising therapy for improvement of prognosis.⁷ Despite candidate selection criteria according to the disease status, recent advances revealed that diagnosis at an early stage is the optimum approach for to achieve favorable prognosis by offering curative treatment options.⁸

To date, approximately 20% of patients with HCC are diagnosed at early stage and benefit from potentially curative ablative treatments.⁹ According to a study involving 5 Dutch centers, surveillance (≥ 2 screening tests during 3 preceding years and at least once of imaging test within 18 months before development of HCC) was found to be an independent prognostic factor that predicts favorable outcomes.¹⁰ A randomized controlled trial including 18,816 patients with hepatitis B virus (HBV) infection demonstrated that surveillance by biannual α -fetoprotein test and ultrasonography examination ameliorated HCC-related mortality from 83.2/100,000 (screening group) to 131.5/100,000 (control group) with a hazard ratio (HR) of 0.63 (95% CI, 0.41 to 0.98), which indicates 37% of decrease in HCC-related mortality.¹¹

Although a validation trial is yet to be carried out, since the only opportunity to provide effective treatments with long-term survival is the detection of the tumor at an early stage, surveillance is crucial predictor for favorable prognosis.

Justification of inclusion criteria for a surveillance program is determined by the risk of HCC life expectancy, and cost-effectiveness.¹² Regarding absence of experimental data, the decision for patient inclusion is based on its efficacy evaluated by heterogeneous designs, indicating that the efficacy of a surveillance program is dependent to incidence of HCC. Accordingly, populations with liver cirrhosis and HBV infection are currently recommended for surveillance.¹³

Ultrasonography and serum tumor markers are the preferred tests for surveillance of HCC based on toleration, availability, non-invasiveness, and sensitivity. Ultrasonography has a reported sensitivity of 60 to 80%, whereas α -fetoprotein was approximately 60% with the most efficient cut-off (10 to 20 ng/mL).^{14,15} Combination of ultrasonography and α -fetoprotein may increase accuracy, but also increases false-positivity and cost. Regarding importance of diagnosis of HCC at early stage, there is an unmet need for a well-made surveillance model to detect early HCC with priority in accuracy and sensitivity; identification of populations at high risk before development of HCC may be ideal if high sensitivity is achieved. In addition, it may prevent up to 6 months of disease progression and improve diagnostic sensitivity, ultimately improving prognosis.

The Prospective Surveillance for Very Early Hepatocellular Carcinoma (PRECAR) trial is designed as an observational multicenter cohort trial to conduct a signature to detect and define very early HCC and individuals at high risk of HCC by analyzing genome sequencing, plasma-

free DNA sequencing, and high-throughput protein expression screening.

Methods and Design

Ethics

The PRECAR trial will be conducted in accordance with the Declaration of Helsinki and current Good Clinical Practice guidelines. The relevant ethics committee approval will be obtained before enrolment of patients. Informed consents will be obtained from all participants before enrollment.

Eligible population

The inclusion and exclusion criteria for the PRECAR trial are described in Table 1. Briefly, two independent cohorts (cirrhosis cohort and HBV infection cohort) will be recruited for surveillance of HCC. The cirrhosis cohort will be consisted of patients with biopsy diagnosis or distinctive clinical characteristics of cirrhotic liver regardless etiology of cirrhosis. For HBV infection cohort, seropositivity of hepatitis B surface antigen is the basic condition for inclusion.

Overview of trial design

PRECAR is a prospective, observational, multicenter trial surveilling development of HCC in patients with cirrhosis or HBV infection. In PRECAR, the aim will be to recruit a total of 10,000 patients (5000 each for the two cohorts) from a minimum of 10 sites. Follow-up will be carried out for eligible patients for collection of demographic, clinical, and serological characteristics and samples for analyses. For those who developed HCC, hepatic resection will be the standard

of care unless unresectable. Data of interest and schedule for the PRECAR trial are summarized in Table 2.

Outcome measures

The primary endpoints of the PRECAR trial include development of HCC, overall survival (OS), and liver-related disease progression (LDP). Secondary endpoints are development of non-HCC malignant neoplasm, such as intrahepatic cholangiocarcinoma, liver resection rate (LRR), and postoperative overall (POS) and relapse-free survival (PRFS) after development of liver malignant neoplasm.

Outcome definitions

HCC – the time from the date of inclusion to development of HCC.

OS – the time from the date of inclusion to death from any cause.

LDP – the time from the date of inclusion to non-malignancy-associated liver-related disease progression or death, whichever is earlier.

Non-HCC – the time from the date of inclusion to development of non-HCC malignant neoplasm.

LRR – the number of malignancy-developed patients whose tumor is resectable without vascular invasion and extrahepatic metastasis.

POS – the time from the date of liver resection to death from any cause.

PRFS – the time from the date of liver resection to tumor progression in the liver or death, whichever is earlier.

Blood collection for biosignature analysis

Peripheral blood samples (25 ml) will be collected from all consenting patients at first 3 follow-up (0, 6th, and 12th month), which will be used to develop a biosignature to stratify patients at high risk for development of HCC. After development of a biosignature, 20 ml of peripheral blood samples will be collected from patients at high risk for HCC at 4th to 7th follow-up for modification and validation of the biosignature.

Statistical analysis

All statistical analyses will be performed using R (<http://www.r-project.org/>) or SPSS (Chicago, IL). Cox hazards proportional model and logistic regression will be applied to screen factors for the inclusion in a biosignature. Correlation test will be performed between results of multivariate Cox and logistic regressions, and false-positive factors will be deleted. After screening covariates, receiver operating characteristic (ROC) curves will be constructed to calculate optimum threshold for setting of cut-off value to define high risk for HCC. Independent demographic and clinical prognostic factors may be combined with the biosignature to improve performance sensitivity and specificity. Predictive signatures for cirrhosis cohort and HBV infection cohort will be developed independently. A correction for multiple testing may be applied.

Discussion

The PRECAR trial will identify predictors for development of HCC and diagnosis of very early

HCC by comparing HCC cases arising from cirrhosis or HBV infection with non-HCC developing cases. To the best of our knowledge, no prospective observational cohort trial has been published with intent to develop a biosignature to stratify patients at high risk for HCC. However, a case control study with similar design (miRNA as a diagnostic tool for HCC) is ongoing in South Africa, where HIV is hyper endemic, thus the etiology of HCC is different from the PRECAR.¹⁶ In addition, ideal aim of the PRECAR trial is to successfully stratify patients who have high potential to develop HCC and carry out intensive follow-up to prevent up to 6 months of disease progression, as well as to offer curative therapeutic options at very early stage to improve prognosis.

Surveillance for HCC has been introduced as an effective strategy to improve prognosis of patients with HCC.¹⁷ However, this field remains to be considered immature due to absence of validation of previous studies and limited accuracy that reduced cost-effectiveness. In recent years, the development of powerful tools, such as genome sequencing, plasma-free DNA sequencing, and high-throughput protein expression screening, suggests that the establishment of a biosignature could improve sensitivity and specificity of current surveillance method. The current surveillance, which is consisted of biannual ultrasonography and α -fetoprotein, reveals limited accuracy, false-positivity, and not efficient in a timely manner. Especially, these are confined to detect already-developed HCC, indicating that if HCC occurred a month after routine surveillance, the tumor will progress for 5 followed months before the next surveillance. Regarding aggressive characteristics and rapid progression, advancement of the tumor is likely to derive patient a worse candidate for curative treatments and deteriorates survival outcomes.

The biosignature developed from PRECAR trial will improve predictive and diagnostic

accuracy for HCC in settings with cirrhosis and HBV infection. During the establishment of the PRECAR biosignature, developmental process of HCC will be further elucidated and translated to improve predictive and diagnostic accuracy. We believe that the PRECAR biosignature will be useful in stratifying patients with cirrhosis or HBV infection at high risk for HCC, as well as in diagnosing HCCs at very early stage.

Trial status

The PRECAR trial is currently ongoing. Patient recruitment will be closed on 15 July 2019 with estimated participant number of 10,000 (5000 for cirrhosis cohort and 5000 for HBV infection cohort). The final analysis will be triggered after 3 years of additional follow-up for enrolled patients for validation of the PRECAR biosignature.

References

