| Physical and clinical assessment | | | | | | | |
| Height | x | | | | | | |
| Weight | x | x | x | x | x | x | x |
| Blood pressure | x | x | x | x | x | x | x |
| Body temperature | x | x | x | x | x | x | x |
| Routine blood test | x | x | x | x | x | x | x |
| Liver function test | x | x | x | x | x | x | x |
| Renal function test | x | op | op | op | op | op | op |
| Electrolyte test | x | op | op | op | op | op | op |
| Blood glucose | x | | | | | | |
| Glycosylated hemoglobin | x | | | | | | |
| Blood lipid | x | | | | | | |
| Hepatitis virus | x | | | | | | |
| HBV DNA ^a | x | x | x | x | x | x | x |
| HIV antibody | x | | | | | | |
| Serum tumor markers | x | x | x | x | x | x | x |
| Ascites ^b | op | op | op | op | op | op | op |
| INR | x | x | x | x | x | x | x |
| Ultrasonography | x | x | x | x | x | x | x |
| Contrast enhanced CT or MRI ^c | x | op | op | op | op | op | op |
| Liver hardness | x | x | x | x | x | x | x |
| Child-Pugh score | x | x | x | x | x | x | x |
| Endpoints evaluation | | x | x | x | x | x | x |
| Sample collection | x | x | x | x | x | x | x |

HBV, hepatitis B virus; HIV, human immunodeficiency virus; INR, international normalized ratio; CT, computed tomography; MRI, magnetic resonance imaging.

^arequired for patients with HBV infection.

^brequired for patients with ultrasonography results indicating ascites.

^crequired for patients with ultrasonography results indicating hepatic nodules.

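### Visit 4–7 blood from high-risk patients is meant both to modify and to validate the biosignature, and no split, lock or test data are stated

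*Combined protocol and SAP*

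**What the plan says.** The blood collection section has two stages. First, 25 ml is "collected from all consenting patients at first 3 follow-up (0, 6th, and 12th month), which will be used to develop a biosignature". Then, once a signature exists, 20 ml is "collected from patients at high risk for HCC at 4th to 7th follow-up for modification and validation of the biosignature".

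The Statistical analysis section uses ROC curves to "calculate optimum threshold for setting of cut-off value to define high risk for HCC", so high risk most naturally means signature-positive. The section also covers Cox and logistic screening, removal of false-positive factors, optional clinical covariates and a possible multiplicity correction. It describes no validation method. Building one signature per cohort is not a development/test split.

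Trial status ties the final analysis, after three further years of follow-up, to validation in enrolled patients. It names no fixed score, patient subset or performance measure, and those patients also supplied the development blood.

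Table 2 has the row "Sample collection | x | x | x | x | x | x | x" with no footnote. The HBV DNA row is also marked at every visit but carries a subgroup footnote. Outcomes are scheduled for all patients from visit 2: "Endpoints evaluation | | x | x | x | x | x | x".

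**The concern.** Two problems follow if the text is applied as it stands and no split is added.

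- **Reuse.** A signature changed to fit a set of patients will look better in those patients than in new ones.
- **Selection.** Blood taken only from signature-positive patients contains no test-negatives. It can support PPV and discrimination within that group, but not cohort-level sensitivity, specificity or NPV for a modified signature.

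The Introduction says that "identification of populations at high risk before development of HCC may be ideal if high sensitivity is achieved". This is motivation and not a success criterion, but sensitivity is a cohort-level quantity and needs HCCs in low-risk patients to be counted.

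**Working it through.** The plan gives no performance target, event rate or dropout, so there is no stated figure to reproduce. Steps 1 and 2 rest on the documents. Steps 3 to 5 are illustrations under labelled assumptions.

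**1. Sources set side by side**

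| Task | Patients | Data | Kept separate? |
|---|---|---|---|
| Develop | all consenting | blood at months 0, 6, 12 | – |
| Modify | high risk | blood at visits 4–7 | not stated |
| Validate (blood section) | high risk | blood at visits 4–7 | not stated |
| Validate (Trial status) | enrolled patients | not stated | not stated |
| Sample collection (Table 2) | no limit shown | visits 1–7 | – |
| Endpoint evaluation (Table 2) | no limit shown | visits 2–7 | – |

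Early blood from everyone plus endpoints in everyone means that the original signature can be tested cohort-wide. A signature that needs visit 4–7 blood cannot be, if the blood section governs.

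**2. Calendar.** The Abstract says "Patients will be recruited for 1 year and follow-up investigation will be performed biannually for 3 years". Trial status closes recruitment on 15 July 2019, so it opened about July 2018.
- First visit 4: study month 18, about January 2020.
- Last month-12 draw: 12 + 12 = study month 24, about July 2020.
- Gap: 24 − 18 = 6 months.

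With even accrual (assumed), 6/12 = 50% of patients reach visit 4 before the last development sample is drawn. If building also waits for that sample and then takes L months (both assumed), the share is (6 + L)/12: 75% for L = 3 and 100% for L = 6.

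**3. Events.** Assumed: 5000 patients per cohort, no dropout, constant hazard, 3-year HCC incidence p of 3% / 9%. Yearly hazard l = −ln(1 − p)/3 = 0.0102 / 0.0314.
- HCC by month 12: 5000(1 − e^(−l)) = about 50 / 155, leaving 4949 / 4845 HCC-free.
- HCC in months 12–36: these numbers × (1 − e^(−2l)), with 1 − e^(−2l) = 2.0% / 6.1%, giving 99 / 295.
- Share of those already known at study month 24: [1 − (1 − e^(−l))/l]/[1 − e^(−2l)] = 0.252 / 0.255, about 25 / 75 HCCs. Nothing in the plan keeps them out of building.

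**4. Selection.** At the cut-off that selects them, all sampled patients are positive on the selecting score. Within that set, sensitivity is 100% and specificity 0% by construction. Assume a binormal score with d = √2·Φ⁻¹(AUC), AUC 0.80 and the top 20% flagged. Cohort sensitivity is then 0.624 / 0.599. So 37 of 99 / 118 of 295 HCCs (38% / 40%) arise in patients who give no visit 4–7 blood. The range is 6–66% over AUC 0.75–0.90 and flagged fraction 10–40%. The flagged group holds 62 HCCs in 990 / 177 in 969 patients, and the score's AUC inside it falls to about 0.67.

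**5. Optimism.** Simulated in that flagged group: add the best 5 of 50, 200 or 1000 candidate markers to the score, refit by logistic regression, and subtract new-patient AUC from same-data AUC (150 replicates). For example, with no informative marker, 1000 candidates and 62 HCCs: 0.786 − 0.605 = 0.181.

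| Informative markers | 62 HCCs | 177 HCCs |
|---|---|---|
| none, best 5 forced in | 0.109–0.181 | 0.053–0.102 |
| five with AUC 0.60 | 0.055–0.133 | 0.011–0.030 |
| five with AUC 0.65 | 0.021–0.045 | 0.005–0.007 |

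With Bonferroni-controlled entry instead, optimism is about 0.00–0.01 when no marker is informative and at most about 0.03–0.04 when some are. If modification only recalibrates the existing score, AUC optimism is zero. If it only re-tunes the cut-off, optimism in Youden's index is about 0.06 / 0.03.

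**The case against.** **The plan does not say that identical patients or draws serve both steps.** It names two purposes for four draws. Modifying on some and validating on others would fit the sentence. This stands: a reader might infer that reuse is planned, but the documents show only that nothing prevents it.

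**The large AUC figures come from a selection rule that the plan does not state.** It speaks of deleting false-positive factors and of a multiplicity correction that may be applied, and it does not define modification. This stands too. The correction is optional and tied to no step, so the gap remains, but 0.1 or more is a worst case and not a forecast.

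**Low-risk HCCs are counted.** A reader might infer that the study cannot estimate sensitivity at all. Table 2 and the early blood from all consenting patients show otherwise for the original signature. The limit applies to a modified one.

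**Reported AUC need not be too high overall.** Restriction to the high-risk group lowers AUC while reuse raises it, so against cohort performance the net bias cannot be signed. The optimism claim holds only within the high-risk group.

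**High-risk sampling has a purpose.** The Discussion wants to "carry out intensive follow-up to prevent up to 6 months of disease progression", and high-risk blood may suit that early-diagnosis aim. This limits what may be claimed from the blood and is no reason against taking it.

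**The Table 2 difference is slight.** The row names no sample type or volume and may lack a footnote. It does not show that everyone gives 20 ml at visits 4–7.

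**Conclusion.** The concern holds as an omission that should be fixed before the final analysis. One set of high-risk blood is assigned to modification and validation, and no split, lock, test data or internal-validation method is stated. Confidence in this is high because it rests on the text alone.

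The consequence is conditional. If the same patients' data tune and test the signature, its within-high-risk performance is optimistic, by an AUC amount from about 0 (strict entry, or many HCCs with strong markers) to above 0.1 (weak markers forced in, few HCCs). These sizes rest on assumed incidence, flagged fraction and marker strength. The 6-month overlap between the first visit 4 and the last month-12 draw follows from the documents; the shares of patients affected need the added assumptions. The difference between the blood section and Table 2 is an item to reconcile.

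**What to change.** **(a) Original signature.** Choose one route and state it.
- *Locked score.* Fix markers, weights and cut-off before the outcomes used to test them are analysed, and give the lock date. Evaluate in all consenting patients HCC-free at month 12, high and low risk, against HCC through month 36. Report sensitivity, specificity, PPV, NPV and calibration per cohort.
- *Resampling.* If later HCC outcomes also build the score, report optimism-corrected estimates, with marker selection and cut-off setting repeated inside bootstrap or leave-one-site-out resampling. Say that this assesses the building procedure.

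**(b) Modified signature.** Do not report performance on the data that modified it. Use resampling that repeats every modification step, or a hold-out of sites or patients named in advance. Label the result as performance within the high-risk group.

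**(c) Text.** Reconcile the blood section with Table 2 on who is sampled at visits 4–7. State how high risk is decided for patients whose visit 4 comes before the signature exists.

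**Cost.** (a) and (b) need analysis-plan text and extra analysis, with no new patients, visits or blood. The figures here use the assumptions in the working.
- The locked route is a real trade-off: building only on HCC known by each patient's own month 12 leaves about 50 / 155 events per cohort. Resampling avoids this and is an equal alternative.
- Cohort-wide testing on 99 / 295 HCCs gives 95% intervals for sensitivity of about 0.53–0.71 / 0.54–0.65.
- Holding out one third of the high-risk group leaves about 62/3 = 21 / 177/3 = 59 HCCs for testing (95% half-width for AUC about 0.13 / 0.08) and fewer for tuning.
- (c) is a text correction. If sampling of everyone is confirmed, it means more draws and storage than the blood section implies.

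Reported performance will probably be less favourable, and any of these internal checks remains weaker than a separate cohort.

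### The text limits visit 4–7 blood to signature-defined high-risk patients while Table 2 samples everyone; if the text governs, part of visits 4–5 may be lost and signature-negative patients give no later samples

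*Combined protocol and SAP*

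**What the plan says.** The section on blood collection for biosignature analysis has two stages. In the first, blood "will be collected from all consenting patients at first 3 follow-up (0, 6th, and 12th month), which will be used to develop a biosignature". The second comes once the signature has been developed: 20 ml samples are "collected from patients at high risk for HCC at 4th to 7th follow-up", to refine and validate the signature.

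High risk is not a separate clinical label. Under Statistical analysis, ROC curves are built after covariate screening "to calculate optimum threshold for setting of cut-off value to define high risk for HCC", so the label is an output of signature development.

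On timing, the Abstract says: "Patients will be recruited for 1 year and follow-up investigation will be performed biannually for 3 years". Trial status adds: "Patient recruitment will be closed on 15 July 2019".

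Table 2 gives a different sampling rule. Its row reads "Sample collection | x | x | x | x | x | x | x", a plain mark at every visit. The same table uses op entries and footnotes for conditional items such as CT/MRI and ascites; the sampling row has neither.

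The documents give no signature lock date, no interim development analysis, no provisional high-risk rule, and no instruction for a patient who reaches visit 4 before the signature is ready.

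**The concern.** There are two separate problems.

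**Timing.** Under the text, a site cannot decide whom to sample at visit 4 until the signature and its cut-off exist. If development waits for all month-12 samples, early enrollees reach visit 4 first. Whether a patient gives a visit 4 or 5 sample would then depend on enrolment date as well as on risk. Blood not drawn at a visit cannot be obtained later.

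**Selection.** Even if the signature were ready on time, sampling only signature-positive patients leaves no later blood from signature-negative patients. Better sensitivity and specificity are stated goals of the signature, and neither can be estimated for the cohort from a set that contains only positives.

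The conflict with Table 2 matters in its own right: two sites could each follow the protocol and collect different samples.

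**Working it through.** The plan gives no figure for this point, so there is none to reproduce. The check is calendar arithmetic.

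**Inputs from the documents**
- Recruitment lasts 12 months (Abstract) and closes on 15 July 2019 (Trial status).
- Visit k falls at month 6(k − 1), which gives 0, 6, 12, 18, 24, 30 and 36, as in Table 2.
- Development samples: months 0, 6 and 12, all consenting patients.
- Planned enrolment: 10,000.

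**Inferred or assumed**
- Recruitment start: closing date minus 12 months, about 15 July 2018. No start date is given.
- Accrual is even over the 12 months.
- Development uses every month-12 sample.
- L is the time in months from the last month-12 draw to a usable signature. The documents give no value, so it is varied from 0 to 12.
- Dropout is ignored.

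**Key dates**
- First patient at visit 4: 15 July 2018 + 18 months = about 15 January 2020.
- Last month-12 sample: 15 July 2019 + 12 months = about 15 July 2020, which is study month 24.
- The development set is therefore complete 6 months after the first visit 4.

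**Share of patients passing a visit too early**

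Let u be enrolment time, uniform on 0 to 12 months. The visit at month m comes before the signature if u + m < 24 + L. The share is (24 + L − m)/12, held between 0 and 1.

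- Visit 4 (m = 18): (6 + L)/12
- Visit 5 (m = 24): L/12
- Visit 6 (m = 30): (L − 6)/12
- Visit 7 (m = 36): (L − 12)/12

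| L (months) | Visit 4 | Visit 5 | Visit 6 | Visit 7 | Mean over the four visits |
|---|---|---|---|---|---|
| 0 | 50% | 0% | 0% | 0% | 12.5% |
| 3 | 75% | 25% | 0% | 0% | 25% |
| 6 | 100% | 50% | 0% | 0% | 37.5% |
| 12 | 100% | 100% | 50% | 0% | 62.5% |

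At L = 0 the visit 4 figure is 0.50 × 10,000 = 5,000 patients. These are shares of patients' visit slots, not counts of lost high-risk samples; the plan does not state what proportion it expects to label high risk.

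**Sensitivity to recruitment length.** For recruitment of A months the visit 4 share is (A − 6 + L)/A. It is zero only if A + L is 6 or less. With A = 9 and L = 0 it is 3/9 = 33%.

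**If Table 2 governs.** No visit 4–7 sample depends on the signature, so the loss is 0%. The most that would be drawn is 4 × 10,000 = 40,000 samples, or 4 × 20 ml = 80 ml per patient.

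**Selection.** No timing assumption is needed here. Sensitivity needs HCC cases among both signature-positive and signature-negative patients. Specificity and negative predictive value need signature-negative patients without HCC. Under the text, visit 4–7 blood comes from signature-positive patients only, so it can inform positive predictive value and performance within that subset, but not these three quantities for the cohort.

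**The case against.** A reader might infer that the signature cannot exist by visit 4 and that the sampling scheme cannot be run at all. The documents do not support that. They say the three early samples are used for development, not that development must wait for the last patient's month-12 draw. A later stage that includes refining the signature is compatible with a first signature built on early enrollees. That answer stands as far as it goes, but no such step is described, and at study month 18 only (18 − 12)/12 = 50% of patients would have a month-12 sample. What is shown is an unspecified timeline with a conditional loss, not an impossibility. The loss is also partial: on the strict reading visit 7 is untouched for lags up to 12 months and visit 6 for lags up to 6 months.

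A reader might also take the lost samples as certain. They are lost only if the text overrides Table 2, and the documents do not say which governs.

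A third tempting reading is that the signature cannot be validated. That too goes beyond the documents. Month 0–12 samples from all consenting patients, with later HCC outcomes, remain available, and Trial status ties validation to the further 3 years of follow-up. The endpoints themselves do not depend on the sampling rule.

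Nor is bias shown to follow from loss by enrolment date. By itself that loss means fewer samples. The selection problem comes from the high-risk restriction.

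Finally, one might use the 30 April 2020 cover date to count patients already past visit 4. The body text does not fit that date: it puts the July 2019 close of recruitment in the future and leaves the 2018 registration date as a placeholder. No such count is relied on here.

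**Conclusion.** The concern holds in a limited form. The text and Table 2 conflict on who is sampled at visits 4–7; this needs no assumption and must be reconciled.

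If the text governs and development uses all month-12 samples, the share of visit 4–7 slots that pass before the signature exists is 12.5%, 25% and 37.5% at lags of 0, 3 and 6 months, falling on visits 4 and 5. These figures rest on the inferred start date, even accrual and the assumed lags. Sequencing and protein screening across a cohort of this size make a lag of zero unlikely, but the documents give no figure.

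The selection problem is independent of timing and is the more serious of the two for interpretation: visit 4–7 blood taken under the text cannot give cohort-level sensitivity, specificity or negative predictive value.

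**What to change.** Amend the blood collection section to agree with Table 2: at visits 4–7, draw and bank the 20 ml sample from every consenting patient, whatever the signature status. State the signature lock date and which patients and visits are used for development.

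After lock, assay a case-cohort set from the bank (all HCC cases plus a random subcohort) and analyse it with inverse-sampling weights. This contains laboratory cost and keeps signature-negative patients in the validation set. Banking must cover everyone: storing blood only from a subcohort and from patients who develop HCC would miss pre-diagnostic samples from future cases outside the subcohort, who cannot be identified at visit 4.

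The cost is up to 40,000 banked draws of 20 ml (80 ml per patient), with processing and storage across at least 10 sites. Table 2 already implies these draws, and they fall at visits where blood is taken anyway, so no visit is added. The sponsor should confirm that consent covers them. Any visit 4 samples already missed cannot be recovered, and the analysis should report how many there are.
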